#### 16.2.2.3. Continuous Secondary Efficacy Endpoints – Total Daily Insulin Divided by Weight

For the analysis of total daily insulin divided by weight, a Mixed-effect Model for Repeated Measurements (MMRM) will be performed based on the PD analysis population using the observed-case data. This model will include the change from baseline variable as the dependent variable, its baseline observed value, age, and time from diagnosis to the first dose as covariates, treatment group (active and placebo), visit, C-peptide AUC, BMI, HbA1C, potency assay, and treatment group-by-visit interaction as fixed effects.

The MMRM modeling and selection procedures described in section 6.2.2.1 will be used to select an appropriate model for this endpoint.

The Least Square (LS) mean estimates will be provided for each treatment group for each visit along with their standard error (SE). The difference of LS means between the treatment groups (active vs. placebo) and associated SE, two-sided 95% CI for each visit, and *p-value* will also be provided only for Visits at Day 150 and Day 360.

#### 16.2.2.4. Continuous Secondary Efficacy Endpoints – Antibody Levels to Glutamic Acid Decarboxylase (GAD65), Insulinoma Associated Protein (IA-2), Zinc Transporter 8 (ZnT8), and Insulin Associated aAb (IAA)

For the analysis of each of the antibody levels to glutamic acid decarboxylase (GAD65), insulinoma associated protein (IA-2), zinc transporter 8 (ZnT8), and insulin associated aAb (IAA), a Mixed-effect Model for Repeated Measurements (MMRM) will be performed based on the PD analysis population using the observed-case data. This

Author:	[name]	Version Number:	2.0
Template No.:	CS_TP_BS016 Revision 6	Version Date:	23Nov2022
Effective Date:	02Dec2019	Reference:	CS_WI_BS005

model will include the change from baseline variable as the dependent variable, its baseline observed value, age, and time from diagnosis to the first dose as covariates, treatment group (active and placebo), visit, C-peptide AUC, HbA1C, BMI, total daily insulin divided by weight, potency assay, and treatment group-by-visit interaction as fixed effects.

The MMRM modeling and selection procedures described in section 6.2.2.1 will be used to select an appropriate model for these endpoints.

The Least Square (LS) mean estimates will be provided for each treatment group for each visit along with their standard error (SE). The difference of LS means between the treatment groups (active vs. placebo) and associated SE, two-sided 95% CI for each visit, and *p-value* will also be provided only for Visits at Day 150 and Day 360.

## 16.3. EXPLORATORY EFFICACY

The exploratory efficacy endpoints analyzed in this SAP are:

- Change from baseline in unstimulated C-peptide of a MMTT.
- Change from baseline in the change in the AUC of C-peptide (Delta AUC) over the first 4 hours of a MMTT.
- Change from baseline in the maximum concentration of C-peptide (Cmax) during a MMTT.
- Change from baseline in the maximum C-peptide levels (Delta Cmax) over the first 4 hours of a mixed meal tolerance test (MMTT).
- Change from baseline in the total area under the curve (AUC) of the stimulated glucose levels over the first 4 hours of a mixed meal tolerance test (MMTT).
- Change from baseline in unstimulated glucose of a MMTT.
- Change from baseline in the change in the AUC of glucose (Delta AUC) over the first 4 hours of a MMTT minus the unstimulated glucose AUC prior to MMTT.
- Change from baseline in the maximum concentration of glucose (Cmax) during a MMTT.
- Change from baseline in the maximum change from baseline concentration (Delta Cmax) of the stimulated glucose levels over the first 4 hours of a mixed meal tolerance test (MMTT)

Author:	[name]	Version Number:	2.0
Template No.:	CS_TP_BS016 Revision 6	Version Date:	23Nov2022
Effective Date:	02Dec2019	Reference:	CS_WI_BS005

### **16.3.1. EXPLORATORY EFFICACY ENDPOINT VARIABLES AND DERIVATIONS**

#### **16.3.1.1. Change from Baseline in unstimulated C-peptide of a MMTT**

Unstimulated C-peptide will be defined as the average of C-peptide at time -10 and 0 minutes of a MMTT.

#### **16.3.1.2. Change from Baseline in the change in AUC of C-peptide (Delta AUC) of a MMTT**

The change in AUC of C-peptide (Delta AUC) will be defined as total AUC C-peptide over the first 4 hours of a MMTT minus the unstimulated C-peptide AUC at time -10 and 0 minutes of the same MMTT.

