#### **8.3.1 Study Days 1, 30 ± 7 days, and 60 ± 7 days**

On the first study day, a 4-hour Mixed Meal Tolerance Test (MMTT) will be performed as part of baseline evaluations. The meal test will be performed in the morning after an overnight fast, with no food or drink (with the exception of water). At the outset, a mixed meal, consisting of High Protein Boost will be administered. Blood samples for C-peptide and glucose will be collected at the following timepoints (in minutes, relative to administration of the mixed-meal): -10, 0, 15, 30, and then at 30 minute-intervals until the last time point of 240 minutes.

1-2 days prior to each study day, study personnel will contact the subject to confirm that they remain in generally good health and that there are no symptoms of acute illness.

Prior to dosing on Study Day 1, a review of eligibility should be performed and confirmed. If, prior to dosing, a randomized subject is not suitable (ineligible) for the trial, that subject will be considered a “randomization failure” and will be replaced.

The following procedures will be performed prior to study drug administration on each dosing day:

- Any changes to medical history including prior treatment, current medicines, and drug

- Focused physical exam including blood pressure, pulse, temperature and weight.
- Laboratory studies including:
  - CMP
  - CBC w diff
  - HbA1c
  - Urine MicroAlbumin panel
  - CrCl (calculation)
- 
- Measurement of auto-antibodies, including:
  - Insulin associated aAb (IAA)
  - Insulinoma associated protein 2 (IA-2, previously known as ICA-512)
  - Glutamic acid decarboxylase (GAD65)
  - Zinc transporter 8 (ZnT8).
- A urine pregnancy test will be collected for females of child-bearing potential.
- Any severe hypoglycemic events occurring since the prior study visit will be recorded. Note that non-severe events are not being collected in the database in this study, but will be monitored by the investigator, consistent with the site's standard of care.

Study drug will be administered during these visits. Laboratory data will be collected prior to initiation of the infusion of study drug.

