#### 16.2.1. SECONDARY EFFICACY ENDPOINT VARIABLES AND DERIVATIONS

##### 16.2.1.1. Change from Baseline in the Area under the Curve (AUC) of the stimulated C-peptide levels over the first 4 hours of a mixed meal tolerance test (MMTT)

The area under the stimulated C-peptide curve (AUC) over the first 4-hour period of a mixed meal glucose tolerance test will be calculated using the trapezoidal rule that is a weighted sum of the C-peptide values over the 240 minutes. Missing C-peptide levels at any given timepoint will not be imputed. In the calculation of the AUC when C-peptide levels are missing, a line will be drawn from the last timepoint with a non-missing C-peptide to the next timepoint with non-missing C-peptide.

Change from baseline in C-peptide AUC will be computed for baseline and for each post-baseline visit where MMTT was a scheduled assessment.

Author:	[name]	Version Number:	2.0
Template No.:	CS_TP_BS016 Revision 6	Version Date:	23Nov2022
Effective Date:	02Dec2019	Reference:	CS_WI_BS005

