#### **16.3.1.4. Change from Baseline in the maximum change from baseline concentration (Delta Cmax) of the stimulated C-peptide levels of a mixed meal tolerance test (MMTT)**

The maximum change from baseline in C-peptide concentration (Delta Cmax) over the first 4-hour period of a mixed meal glucose tolerance test is defined as the maximum concentration of C-Peptide during the MMTT test minus the baseline concentration of C-Peptide, which is calculated as the average of C-Peptide at time -10 min and 0 min of the same MMTT test. Missing C-peptide levels at any given timepoint will not be imputed.

The maximum delta C-peptide Cmax will be computed for baseline and for each post-baseline visit where MMTT was a scheduled assessment.

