#### **16.3.1.7. Change from Baseline in the change in AUC of glucose (Delta AUC) of a MMTT**

The change in AUC of glucose (Delta AUC) over the first 4-hour period of a MMTT will be defined using the approach described in Section 16.3.1.2.

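### Taken literally, Delta AUC for C-peptide and glucose subtracts only 10 minutes of fasting area from a 240-minute total, so about 96% of the basal area stays in

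*Combined protocol and SAP*

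**What the plan says.** All section numbers are from SAP v2.0 unless stated.

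- **Delta AUC, C-peptide (16.3.1.2).** The first term is "total AUC C-peptide over the first 4 hours of a MMTT". The second term is taken off it: "minus the unstimulated C-peptide AUC at time -10 and 0 minutes of the same MMTT". SAP v1.0 has the same text under the same number.
- **Total AUC (16.2.1.1).** It is "calculated using the trapezoidal rule that is a weighted sum of the C-peptide values over the 240 minutes". The SAP does not divide it by time.
- **Sampling (protocol 8.3.1, repeated in 8.6).** Samples are drawn at minus "10, 0, 15, 30, and then at 30 minute-intervals until the last time point of 240 minutes". The only pre-meal interval is therefore 10 minutes long.
- **Fasting level (16.3.1.1).** "Unstimulated C-peptide will be defined as the average of C-peptide at time -10 and 0 minutes of a MMTT". This is a concentration and a separate endpoint.
- **Delta Cmax (16.3.1.4).** The peak "minus the baseline concentration of C-Peptide, which is calculated as the average of C-Peptide at time -10 min and 0 min" of the same test.
- **Delta AUC, glucose.** Section 16.3.1.7 says that it "will be defined using the approach described in Section 16.3.1.2". The bullet in 16.3 words it as Delta AUC over the first 4 hours "minus the unstimulated glucose AUC prior to MMTT".

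Section 2.3 lists nine exploratory endpoints, of which these are two. Section 16.3.2.1 summarises observed values, changes from baseline and percent changes by visit, with no model or test.

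**The concern.** Subtracting an unstimulated AUC from a total AUC has one evident purpose: to leave the part of the curve that is due to the meal. That works only if both areas cover the same length of time. Here one term covers 240 minutes and the other, on its plain reading, covers 10.

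Fasting C-peptide, fasting glucose and both total AUCs are already reported as endpoints of their own. Delta AUC adds information only if it removes the fasting component. If it does not, it repeats total AUC under another name, and a shift in fasting level with no change in meal response appears as a change in Delta AUC. A programmer who follows the text exactly would produce that variable.

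**Working it through.** The plan gives no figure for Delta AUC, so there is nothing to reproduce. The check is trapezoidal arithmetic on the protocol's sampling times. C-peptide is in pmol/mL, as in protocol 9.8.2.

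**Notation.** b = mean of the -10 and 0 minute values. AUC = trapezoidal area from 0 to 240 minutes.

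- As written: D_lit = AUC - 10 x b
- Basal level over the same period: D_inc = AUC - 240 x b
- Hence D_lit = D_inc + 230 x b

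**Step 1. Share of the basal area removed.** 10/240 = 4.2%, so 230/240 = 95.8% is left. This holds for any fasting level and any curve.

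**Step 2. Flat curve, no meal response.** With an assumed b of 0.4, AUC = 240 x 0.4 = 96. D_inc = 96 - 96 = 0. D_lit = 96 - 4 = 92.

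**Step 3. Observed values on an assumed curve.** Take increments above fasting of 0, 0.10, 0.25, 0.45, 0.50, 0.45, 0.38, 0.30, 0.22 and 0.15 at 0, 15, 30, 60, 90, 120, 150, 180, 210 and 240 minutes. Their trapezoidal area is 78.375.

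| Assumed b | AUC | D_lit | D_inc | D_lit / D_inc | D_lit / AUC |
|---|---|---|---|---|---|
| 0.2 | 126.375 | 124.375 | 78.375 | 1.59 | 98.4% |
| 0.4 | 174.375 | 170.375 | 78.375 | 2.17 | 97.7% |
| 0.6 | 222.375 | 216.375 | 78.375 | 2.76 | 97.3% |

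**Step 4. Absolute change from baseline.** Change in D_lit = change in D_inc + 230 x change in b.

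- Fasting rises by an assumed 0.1, meal response unchanged: D_lit changes by 230 x 0.1 = +23.0, total AUC by 240 x 0.1 = +24.0 and D_inc by 0. This does not depend on curve shape.
- Fasting unchanged: the extra term is 0 and the two definitions give the same change.

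**Step 5. Percent change.** Use the b = 0.4 row, hold fasting constant and halve the meal increment from 78.375 to 39.1875. D_inc falls by 50%. D_lit goes from 170.375 to 131.1875, a fall of 39.1875/170.375 = 23.0%. So percent change is distorted even when fasting is stable.

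**Step 6. Other readings.**

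- Total area taken from -10 to 240 minutes: subtracting the 10-minute area leaves 100% of the basal part of 0-240.
- Each area divided by its own length: AUC/240 - b = D_inc/240, which is sound.
- Fasting level extended over 240 minutes: this is D_inc, which is sound.

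The SAP states neither of the two sound readings.

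**Glucose.** The factor of 230 minutes carries over. An assumed rise of 1 mmol/L in fasting glucose with an unchanged meal response moves D_lit by 230 mmol/L x min.

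**The case against.** The strongest reply is that the SAP never gives the subtracted area a length. The 10 minutes are inferred from two named time points and the trapezoidal rule. Section 16.3.1.1 has just defined the unstimulated level as an average of those samples. Delta Cmax subtracts that same average like for like, and protocol 9.8.2 has a time-averaged AUC (AUC/240). The authors may well have meant the fasting level over 240 minutes. This stands as a caution about intent. It does not rescue the text: the AUC/240 form is not carried into the SAP derivation, no sentence extends the basal term, and the glucose bullet places the area before the test.

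A second reply is that the endpoint is a change from baseline. A reader might infer from Step 3 that the treatment signal is inflated 1.6 to 2.8 times. The documents do not support that. Those ratios apply to observed values and rest on one assumed curve shape with three assumed fasting levels. In the absolute change the basal term cancels when fasting is stable.

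A third reply is that little depends on these endpoints. Section 2.3 says the protocol does not define them. They are descriptive only, and a fasting shift would be visible in the separate fasting endpoints. Delta Cmax is already corrected properly. This also stands, and it limits the weight of the point.

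**Conclusion.** The definition is wrong as written and should be corrected, but the consequence is small. Followed literally, it leaves 95.8% of the basal area in Delta AUC for both C-peptide and glucose, whatever the fasting level. Three effects follow:

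- observed values are too large by 230 x the fasting level;
- percent changes are distorted;
- absolute changes from baseline are wrong by 230 x the change in fasting level, and are right when that change is zero.

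The result rests on the trapezoidal rule applying to the two fasting samples and on the total AUC starting at 0 minutes. The 0.1 pmol/mL shift and the curves are assumptions for illustration.

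A reader might go further and infer that the C-peptide efficacy analysis is compromised. It is not: the MMRMs in 16.2.2 use total AUC, HbA1c, weight-adjusted insulin and autoantibodies, and Delta AUC enters none of them. Nor do the documents show that the Month 5 outputs are wrong, because they do not say how Delta AUC was programmed.

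**What to change.** 1. In 16.3.1.2, define Delta AUC as AUC(0-240) minus 240 x the mean of the -10 and 0 minute values of the same test, and state that the total area starts at 0 minutes. Section 16.3.1.7 then carries this to glucose.
2. Align the glucose bullet in 16.3, which now subtracts a fasting area from a quantity that is already called a difference.
3. Check the program behind the Month 5 outputs. If the literal formula was used, rederive both endpoints and record the change as a correction made after unblinding. If the 240-minute form was used, record that instead.

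The text change is one definition and one bullet, with one derivation line in the program and no new data. Section 4.4 already foresees a SAP amendment before the Month 24 lock, which could carry it. The further cost depends on step 3. SAP v1.0 has the same wording, section 4.2 dates unblinding to 17 May 2022 and delivery of the v1.0 analyses to 10 June 2022, and Month 5 and Day 360 outputs must use one definition.

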#### **16.3.1.3. Change from Baseline in the maximum concentration of C-peptide (Cmax) of a MMTT**

The maximum concentration of C-peptide will be defined as the maximum C-peptide value over the first 4 hours of a MMTT.

#### **16.3.1.4. Change from Baseline in the maximum change from baseline concentration (Delta Cmax) of the stimulated C-peptide levels of a mixed meal tolerance test (MMTT)**

The maximum change from baseline in C-peptide concentration (Delta Cmax) over the first 4-hour period of a mixed meal glucose tolerance test is defined as the maximum concentration of C-Peptide during the MMTT test minus the baseline concentration of C-Peptide, which is calculated as the average of C-Peptide at time -10 min and 0 min of the same MMTT test. Missing C-peptide levels at any given timepoint will not be imputed.

The maximum delta C-peptide Cmax will be computed for baseline and for each post-baseline visit where MMTT was a scheduled assessment.

#### **16.3.1.5. Change from Baseline in the AUC of the stimulated glucose of a MMTT**

The area under the stimulated glucose curve (AUC) over the first 4-hour period of a mixed meal glucose tolerance test will be calculated the trapezoidal rule as described in Section 16.2.1.

#### **16.3.1.6. Change from Baseline in unstimulated glucose of a MMTT**

Unstimulated glucose will be defined using the approach described in Section 16.3.1.1.

Author:	[name]	Version Number:	2.0
Template No.:	CS_TP_BS016 Revision 6	Version Date:	23Nov2022
Effective Date:	02Dec2019	Reference:	CS_WI_BS005

#### **16.3.1.7. Change from Baseline in the change in AUC of glucose (Delta AUC) of a MMTT**

The change in AUC of glucose (Delta AUC) over the first 4-hour period of a MMTT will be defined using the approach described in Section 16.3.1.2.

#### **16.3.1.8. Change from Baseline in the maximum concentration of glucose (Cmax) of a MMTT**

The maximum glucose concentration (Cmax) over the first 4-hour period of a MMTT will be derived using the approach described in Section 16.3.1.3.

#### **16.3.1.9. Change from Baseline in the maximum change from baseline concentration (Delta Cmax) of the stimulated glucose levels of a MMTT**

The maximum change from baseline in glucose concentration (Delta Cmax) over the first 4-hour period of a MMTT will be derived using the approach described in Section 16.3.1.4.

### **16.3.2. ANALYSIS OF EXPLORATORY EFFICACY ENDPOINTS**

#### **16.3.2.1. Continuous Exploratory Efficacy Endpoints**

Observed and change from baseline for all exploratory endpoints will be summarized by treatment group and visit. Univariate summaries of the observed values and changes from baseline (both observed and percent change) will be generated by study visit.

## **17. SAFETY ENDPOINTS**

All safety summaries will be presented by treatment group based on the SAF population. There will be no statistical comparisons between the treatment groups for safety data.

### **17.1. ADVERSE EVENTS**

- Prior adverse events (AEs) are defined as any AE that started or worsened in severity on or after the date of signed informed consent but before the first dose of study drug.
- Treatment-emergent AEs (TEAEs) are defined as any AE that starts on or after the first dose of study

Author:	[name]	Version Number:	2.0
		Version Date:	23Nov2022
Template No.:	CS_TP_BS016 Revision 6	Reference:	CS_WI_BS005
Effective Date:	02Dec2019		

medication. This includes events that start within 30 days following the last dose.

- Post-treatment AEs are defined as adverse events that start more than 30 days following the last dose.

See [APPENDIX 1](#) for handling of partial dates for AEs. In the case where it is not possible to define an AE as treatment emergent or not, the AE will be classified by the worst case; i.e. treatment emergent.

AEs will be coded using the MedDRA dictionary, version 22.0.

An overall summary of number and percentage of subjects within each of the categories described in the sub-sections below will be provided by treatment group based on the SAF analysis population. Should a subject experience multiple events within a category, the subject will be counted only once for that category. Each adverse event summary table will include a sub-table summarizing TEAEs and a sub-table summarizing post-treatment AEs.

All AEs (prior, TEAE, and post-treatment) will be listed. The listing will include a column for relatedness (see section 17.1.1.2), a column for outcome, and a column to identify potential dose-limiting toxicities as collected on the AE CRF page. Listings of subsets of AEs will include these columns as well.

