**Duration of treatment:**

There are three pre-defined periods in this study.

- Screening and cell collection period will last up to 3 months.
- Treatment period will consist of 3 doses, each ~30 days apart (Baseline, Month 1, Month 2) and a 1-month post-last dose assessment period (through Month 3). Thus, the treatment period is defined to be 3 months in duration.
- Post-Treatment Follow-up Period will extend approximately 21 additional months (and thus through Month 24 of the study).

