### 7.1 Administration of Study Drug.

A study drug handling manual and study drug administration manual (Manual of Operating Procedures, ie, MOP) describes study drug management in detail.

Administration of the treatment regimen is as follows:

- On Study Day 1, the subject will receive study treatment (the AVT001 or placebo infusion).
- The interval between injections will be 30 (+/- 7) days. Subsequent injections will be at Study Day 30 and 60 (each ± 7 days and at least 21 days apart), for a total of 3 i.v. injections.

Subjects will be observed for at least 2 hours post-end of each infusion. Safety and tolerability assessments will be performed, including measurement of vital signs. Local tolerability at the infusion site (such as pain, swelling, tenderness, and erythema) will be assessed via adverse event reporting. Please refer to the study drug handling manual and study drug administration manual (Manual of Operating Procedures, ie, MOP) for details on monitoring, Receiving, Storage, Dispensing and Return.

A study drug handling manual and study drug administration manual (Manual of Operating Procedures, ie, MOP) describes study drug management in detail.

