### 9.5 Adverse Events

Adverse events will be reported using the MedDRA coding dictionary. Tabulations will include an overall incidence of at least one adverse event, incidence within body system, and incidence by preferred term. Each subject may only contribute once (ie, first occurrence) to each of the incidence rates, regardless of the number of occurrences. The incidence of adverse events will be presented as follows:

- The incidence of treatment-emergent adverse events (TEAEs), ie, those events that start on or after the first dose of study medication, will be tabulated by treatment for the Treatment Phase. This will include events starting within 30 days following the last dose.
- The incidence of post-treatment events (those events that start more than 30 days following the last dose) will be tabulated.

Subjects with serious adverse events (including deaths) and subjects who discontinue due to adverse events will be listed. Subjects who have other significant serious adverse events deemed to be of special interest because of clinical importance will also be listed.

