## 2. STUDY OBJECTIVES AND ENDPOINTS

### 2.1. PRIMARY OBJECTIVE AND ENDPOINTS

Objectives	Endpoints
To determine the safety and tolerability profile of three doses of AVT001 (as compared to placebo) in T1D subjects within-vitro -reversible defects in the CD8+ T cell regulatory system.	Incidence of treatment-emergent adverse events (TEAEs).  Clinically significant changes from baseline in clinical laboratory parameters.  Incidence and severity of local IV-site reactions.  Changes from baseline in vital signs and electrocardiograms.  Incidence of severe hypoglycaemic events.

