#### **17.1.4. AEs LEADING TO DISCONTINUATION OF STUDY DRUG**

TEAEs leading to permanent discontinuation of study drug are those events recorded as “Drug Permanently Discontinued” on the AE pages of the eCRF. A summary of TEAEs leading to permanent discontinuation of study drug by SOC and PT will be prepared. A sub-table of post-treatment AEs leading to discontinuation of study drug by SOC and PT will also be prepared.

A listing of all AEs leading to permanent discontinuation of study drug will be provided.

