## APPENDIX 1. PARTIAL DATE CONVENTIONS AND MISSING DATA IMPUTATION

### ALGORITHM FOR PRIOR ADVERSE EVENTS, TREATMENT-EMERGENT ADVERSE EVENTS, AND POST-TREATMENT ADVERSE EVENTS

START DATE	END DATE	ACTION
Known	Known/Partial/ Missing	If (AE start date < study drug start date) or AE is a pre-initial dose event, then PRAE.  If study drug start date $\leq$ AE start date and AE start date $\leq$ last drug date_30 and AE is not a pre-initial dose event, then TEAE.  If study drug start date $\leq$ AE start date and AE start date $>$ last drug date + 30 then PTAE
Partial, but known components show that AE started before study drug start date or AE is a pre-initial dose event	Known/Partial/ Missing	PRAE
Partial and known components show that AE started on or after study drug start date	Known/Partial/ Missing	Impute missing AE start day as the first of the month or the first study drug dose date, whichever is later.  If (AE start date < study drug start date) or AE is a pre-initial dose event, then PRAE.  If study drug start date $\leq$ AE start date and AE start date $\leq$ last drug date+30 and AE is not a pre-initial dose event, then TEAE.  If study drug start date $\leq$ AE start date and AE start date $>$ last drug date+30 then PTAE

Note: If an AE started prior to first dose of study drug but worsened after treatment started, it will be reported as a separate adverse event with a new AE start date. A pre-initial dose event is defined as an AE that is entered in the

Author:	[name]	Version Number:	2.0
		Version Date:	23Nov2022
Template No.:	CS_TP_BS016 Revision 6	Reference:	CS_WI_BS005
Effective Date:	02Dec2019		

EDC as occurring prior to infusion (Month 0, Day 1).

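### An adverse event that ends treatment just before a late-scheduled infusion falls outside the TEAE count, while the same event in a subject who is dosed again is counted; the effect is small but easily removed

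*Combined protocol and SAP*

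**What the plan says.** TEAE incidence is the first primary endpoint listed in SAP v2.0 section 2.1. Section 17.1 starts the TEAE window at the first dose and says of its end: "This includes events that start within 30 days following the last dose". Anything later goes to a second category: "Post-treatment AEs are defined as adverse events that start more than 30 days following the last dose". Appendix 1 turns this into the programming rule. An event starting on or after the first dose, with a start date beyond "last drug date + 30 then PTAE", is post-treatment.

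The SAP does not spell out whether the last dose means the last one given or the last one planned. Appendix 1 works from a last drug date, and section 14.1 takes administration dates from the eCRF dosing page, so the natural reading is the last dose given.

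Protocol Amendment 3 section 7.1 sets the spacing: "The interval between injections will be 30 (+/- 7) days". It also places infusions 2 and 3 at Study Days 30 and 60, each with a 7-day window either side and at least 21 days between doses.

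SAP section 17.1.4 plans a table of TEAEs that led to permanent discontinuation and adds: "A sub-table of post-treatment AEs leading to discontinuation of study drug by SOC and PT will also be prepared".

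**The concern.** The counting window closes 30 days after an infusion, but the next infusion may be due later than that. Suppose an event begins in between. If the subject goes on to the next infusion, that infusion becomes the last dose, the window moves forward and the event is a TEAE. If the event itself ends treatment, the previous infusion remains the last dose and the same event, on the same day, is post-treatment. Classification then depends on the consequence of the event rather than on its timing relative to exposure. The subjects affected are those whose event was serious enough to end dosing.

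Nothing in section 17.1 repairs this. The worst-case rule there applies only when an event cannot be classified, and an event with a known start date can be. The sub-table in section 17.1.4 shows that the category is provided for. Only a subject with an infusion outstanding can have study drug stopped, so in logic only early stoppers can fill it.

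At stake is the first primary endpoint of a small first-in-man trial, with an error that runs against showing harm.

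**Working it through.** **The plan's own figure.** SAP section 7.1 claims at least 80% probability of observing one or more TEAEs among 14 AVT001 subjects at a true incidence of 12%. 1 − 0.88^14 = 0.833, or 83.3%, so the claim is met.

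**Infusion 1 to infusion 2.** Infusion 1 is on Day 1, so the window closes 30 days later, on Day 31. Infusion 2 may be given on Days 23 to 37, which is 15 permitted dates. If it is due on Day 37, onset on Days 32 to 36, or on Day 37 before the infusion, is uncovered: 37 − 31 = 6 onset days. A gap opens for the 6 permitted dates from Day 32 to Day 37 and for none of the other 9.

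**Infusion 2 to infusion 3.** The interval rule allows at most 30 + 7 = 37 days, for example Day 30 to Day 67. Uncovered: 37 − 30 = 7 onset days.

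**Nominal schedule.** Days 1, 30 and 60 give intervals of 29 and 30 days. Neither exceeds 30, so the gap is zero.

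**Classification of one event.** Take an event starting on Day 34, with infusion 2 due on Day 37.

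| What happens next | Last dose given | Cut-off | Class |
|---|---|---|---|
| Infusion 2 given on Day 37 | Day 37 or later | Day 67 or later | TEAE |
| Event ends treatment | Day 1 | Day 31 | Post-treatment |

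**Size.** If the subject has no other TEAE, AVT001 incidence changes by 1/14 = 7.1 points on the design number, or 1/16 = 6.3 points on the number to be randomized to AVT001. If the subject has another TEAE, overall incidence does not change; only the counts by preferred term, severity and discontinuation do.

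**Effect on the 83.3%, for illustration only.** Let f be the share of AVT001 subjects with a TEAE who lose that status. The documents give no value for f. The probability is 1 − (1 − 0.12 × (1 − f))^14, which is 81.6% at f = 5%, 79.8% at f = 10% and 73.3% at f = 25%. It drops below 80% once f exceeds 9.5%.

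**The case against.** The best defence is that a window of last dose plus 30 days is a reasonable, exposure-based choice, set in advance in both documents. The trigger is also narrow. The next infusion must be due more than 30 days after the previous one, the event must begin in those last few days, and it must end treatment. An event that begins within 30 days of the last dose stays a TEAE even if the subject stops. Nothing is concealed. Each AE summary table carries a post-treatment sub-table by arm, all events leading to discontinuation are listed whatever their timing, and safety comparisons are descriptive. The sub-table in section 17.1.4 may simply follow from that general layout. All of this stands and limits the size of the point. It does not explain why the same event on the same day should be classified by whether it stopped dosing.

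Three stronger readings are tempting but not supported.

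- *The SAP contradicts the protocol.* Protocol section 9.5 says TEAEs "will be tabulated by treatment for the Treatment Phase", and the synopsis says of the treatment period: "Thus, the treatment period is defined to be 3 months in duration". A reader might infer a fixed three-month window. But section 9.5 and the synopsis safety text go on to state the same 30-day cut-off, and the three months are themselves built as three doses plus one month after the last. The SAP copies the protocol's rule.
- *The gap can reach 14 days.* Visit windows alone would allow Day 23 to Day 67, which is 44 days, and 44 − 30 = 14. The interval rule in section 7.1 applies as well and caps the interval at 37 days.
- *Early stopping makes an arm look much safer.* The TEAE window is about Days 1–31 after one infusion and Days 1–90 after three. With a constant hazard, 12% over 90 days becomes 1 − 0.88^(31/90) = 4.3% over 31 days. The plan does not state 12% as a 90-day rate, a constant hazard is doubtful for someone spared two infusions, and one such subject among 14 shifts expected arm incidence by only (12 − 4.3)/14 = 0.55 points.

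**Conclusion.** The point holds in a narrow form. For onset in the last 6 days before a late infusion 2, or the last 7 before a late infusion 3, an event that ends treatment leaves the TEAE count, while the same event in a subject who continues stays in it. The rule sits in both the SAP and the protocol, so this is a weakness in a shared definition and not an inconsistency between documents.

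The effect is small: 6 to 7 points of AVT001 TEAE incidence per affected subject with no other TEAE, and nothing if infusions run on nominal days. No test or p-value is touched. The conclusion assumes that the last dose means the last dose given. The documents do not say whether any subject stopped early, so the number affected is unknown and may be zero. It is still worth correcting, because it concerns the first primary endpoint and the events at issue are those that ended treatment.

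**What to change.** SAP section 4.4 promises an amendment before the final database lock. Use it for the following.

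1. In section 17.1 and Appendix 1, state that any event starting on or after the first dose (and not flagged as pre-initial-dose), and recorded on the AE page as having led to permanent discontinuation of study drug, is a TEAE whatever the number of days since the last dose.
2. Keep last dose plus 30 days as the main window for all other events.
3. Add one supplementary table by arm of all events from first dose through the Day 90 visit in all dosed subjects. Note who has incomplete follow-up: Protocol section 11.3.1 ends AE reporting at early termination if that comes sooner, and section 6.3 promises only best efforts afterwards, so unobserved time must not read as event-free.
4. Record the change in section 3.3 as made after the Month 5 unblinding of 17 May 2022, and show results under the current classification too. Keep the sub-table in section 17.1.4 for that purpose.

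Replacing the window outright with a fixed Day 90 limit is not needed. It would redefine the first primary endpoint after unblinding, for a small gain.

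The cost is a few lines of wording, one condition in the derivation and one extra table, all from data already collected. The TEAE count may come out slightly less favourable.
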